3.2 Exclusion Criteria

Late rollover subjects (ie, those who were unable to rollover from Trial 405-201-00013 or Trial 405-201-00014 due to the inability of an in-person baseline visit in Trial 405-201-00015) will be excluded if they meet any of the exclusion criteria presented in Table 3.2-1.

| Tab | le 3.2-1 Exclusion Criteria for Late Rollover Subjects From Trial 405-201-00013 or Trial 405-201-00014 |
|-----|--|
| 1. | Subjects who, during the double-blind phase 3 trial (ie, Trial 405-201-00013 or Trial 405-201-00014), experienced, in the opinion of the investigator, poor tolerability to the IMP or whose safety assessments resulted in new concerns that would suggest the subject may not be appropriate for a 52-week treatment with IMP. |
| 2. | Subjects who have demonstrated noncompliance, based on the investigator's judgment, to follow trial procedures during the course of their participation in the double-blind phase 3 trial (ie, Trial 405-201-00013 or Trial 405-201-00014). The medical monitor should be contacted if the investigator is unsure of a subject's eligibility. |
| 3. | Females who have a positive pregnancy test result prior to receiving IMP. |
| 4. | Sexually active males or FOCBP who do not agree to practice 2 different methods of birth control or remain abstinent during the course of the trial and for 30 days after the last dose of IMP for female subjects, and 90 days after the last dose of IMP for male subjects and their partners who are FOCBP. Unless the subject is sterile (ie, females who have had a bilateral oophorectomy or hysterectomy or who have been postmenopausal for at least 12 consecutive months; or males who have had a bilateral orchiectomy) or remains abstinent, 2 of the following precautions must be used: vasectomy, tubal ligation, vaginal diaphragm, intrauterine device, birth control pills, birth control injection, birth control implant, birth control patch, condom with spermicide, or sponge with spermicide. Male subjects who do not agree to refrain from donating sperm from screening through 90 days after the last dose of IMP will also be excluded. |
| 5. | Following responses from the "Since Last Visit" version of the C-SSRS (subjects should reference their last visit on Trial 405-201-00013 or Trial 405-201-00014): Subjects with a response of "Yes" on the C-SSRS Suicidal Ideation Item 4 (Active Suicidal Ideation with Some Intent to Act, Without Specific Plan) at entry, OR Subjects with a response of "Yes" on the C-SSRS Suicidal Ideation Item 5 (Active Suicidal Ideation with Specific Plan and Intent) at entry, OR Subjects with a response of "Yes" on any of the 5 C-SSRS Suicidal Behavior Items (actual attempt, interrupted attempt, aborted attempt, preparatory acts, or behavior) at entry, OR Subjects who, in the opinion of the investigator (including consideration of responses on the C-SSRS throughout Trial 405-201-00013 or Trial 405-201-00014), present a serious risk of suicide. |
| 6. | Subjects with a newly developed psychiatric or medical condition that would be exclusionary under the criteria listed for Trial 405-201-00013 or Trial 405-201-00014. |
| 7. | Subjects that have a positive alcohol test (via breathalyzer or blood), or a positive drug screen for cocaine or other illicit drugs (excluding marijuana). Subjects with a positive drug screen for confirmed prescription medications at baseline will not be permitted to continue participation in Trial 405-201-00015. NOTE: Subjects that test positive for marijuana may be permitted to be enrolled if they have no evidence of a substance use disorder, and if they agree to refrain from use for the duration of the trial. Allowance for subjects testing positive for marijuana at screening requires explicit approval from the medical monitor. |
| 8. | Any new or developing safety concerns related to vital signs in the opinion of the investigator during the baseline visit. |

Confidential - Proprietary Information

14

| Tabl | Table 3.2-1 Exclusion Criteria for Late Rollover Subjects From Trial 405 201 00013 or Trial 405 201 00014 | | | | | | |
|-------|--|--|--|--|--|--|--|
| | 1 mai 405-201-00015 of 1 mai 405-201-00014 | | | | | | |
| 9. | The following laboratory test and ECG results are exclusionary: | | | | | | |
| | 1) Platelets $\leq 75000/\text{mm}^3$ | | | | | | |
| | 2) Hemoglobin $\leq 9 \text{ g/dL}$ | | | | | | |
| | 3) Neutrophils, absolute $\leq 1000/\text{mm}^3$ | | | | | | |
| | 4) AST > $2 \times$ upper limit of normal | | | | | | |
| | 5) ALT > 2 \times upper limit of normal | | | | | | |
| | 6) Creatinine $\geq 2 \text{ mg/dL}$ | | | | | | |
| | 7) HbA1c \geq 7% | | | | | | |
| | 8) Abnormal free T4 (free T4 is measured only if result for TSH is abnormal) | | | | | | |
| | 9) QTcF and/or QTcB > 450 msec for males or > 470 msec for females | | | | | | |
| | NOTE: In addition, subjects should be excluded if they have any other abnormal laboratory tests, vital sign results, or ECG findings which, in the investigator's judgment, are medically significant and would impact the safety of the subject or the interpretation of the trial results. Tests with abnormal results should be repeated to ensure reproducibility of the abnormality before excluding a subject based on the criteria noted above. The medical monitor should be contacted if the investigator is unsure of a subject's eligibility. | | | | | | |
| 10. | Subjects receiving any of the prohibited medications within the specified period prior to the first | | | | | | |
| | dose of IMP or who would be likely to require prohibited concomitant therapy during the trial | | | | | | |
| | (refer to Section 4.1 of the protocol). | | | | | | |
| 11. | Subjects who have previously been enrolled in this trial and subsequently withdrawn. | | | | | | |
| 12. | Any subject who, in the opinion of the investigator, should not participate in the trial. | | | | | | |
| ALT = | alanine aminotransferase; AST = aspartate aminotransferase; FOCBP = females of childbearing | | | | | | |

potential; QTcB = QT interval corrected for heart rate by Bazett's formula; QTcF = QT interval corrected for heart rate by Fridericia's formula; $T_4 =$ free thyroxine.

4 Trial Procedures

If an in-person screening and baseline visit cannot be performed, then the subject cannot continue or be enrolled in the trial. The postbaseline visits should also be conducted in person; however, they may be conducted remotely due to COVID-19 restrictions. Subjects may miss up to 2 consecutive in-person assessments due to COVID-19 restrictions. The medical monitor must be consulted if the subject will miss more than 2 consecutive visits and determine whether or not the subject can continue on IMP. During the trial, if efficacy/safety assessments are unable to be obtained, the subject may continue in the trial; however, if a subject is unable to collect a urine pregnancy test, the medical monitor must be contacted. At all postbaseline visits conducted remotely, the assessments will be done by telephone or video chat.

4.1 Safety Assessments

4.1.1 Vital Signs

Blood pressure, heart rate, weight, and temperature may be measured as described in the protocol at the time points defined in this COVID-19 Addendum Schedule of Assessments (Table 1.2-1 and Table 1.2-2) with the following changes:

- Subjects will be asked to use their own collection device, if available. (Device(s) may be provided to subjects).
- Subjects will be instructed to be as consistent as possible regarding the time of day the measurement is taken, and to notify the site staff of the measurement results via telephone, or other means, on the appropriate visits.
- Site staff will be instructed to record the measurement in eSource, and if there are believed to be any errors, inconsistencies, or safety concerns with the reported home measurement, the medical monitor should be notified.

For subjects who cannot obtain vital signs, a maximum of 2 consecutive months of missed vital sign assessments are permitted. If a subject cannot be seen in the clinic or cannot obtain vital signs remotely through available collection devices after that point, the medical monitor must be consulted to ascertain whether the subject should be discontinued from the trial.

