3.7.4.4 Vital Signs

Vital signs including systolic blood pressure and diastolic blood pressure, heart rate, respiratory rate, and body temperature will be measured at the time points described in the Schedule of Assessments (Table 3.7-1 and Table 3.7-2 for rollover subjects and Table 3.7-3 and Table 3.7-4 for de novo subjects). Blood pressure and heart rate measurements will be made in the supine and standing positions after the subject has been in each position for at least 3 minutes. The supine measurements will be performed first followed by the standing measurements. Temperature and respiratory rate will be taken with the subject in the supine position. At baseline, predose vital signs will be measured before dosing. Vital signs are to be completed before any blood is drawn.

Subjects should be monitored for potentially clinically significant vital signs values (Appendix 3). Abnormal results that are deemed clinically significant should be repeated to ensure reproducibility of the abnormality. Any abnormalities considered by the investigator to be clinically significant are to be recorded as AEs on the AE eCRF (Section 5.2).

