#### 8.1 COVID-19 Related Supplementary Analyses

Summary statistics for mean and mean change from baseline in AISRS Total Score, by trial visit and at the last visit (i.e., Week 52/ET) and by visit type (face-to-face vs. virtual) based on the Efficacy Sample will be provided by parent study treatment group for rollover subjects, de novo subjects and overall.

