## 9.3 Physical Examination and Vital Signs

Summary statistics for changes from baseline in vital signs will be provided for the Safety Sample. By-patient listings will be provided for physical examination.

Potentially clinically relevant vital signs measurements identified in the open-label treatment phase for the Safety Sample will be listed and summarized. Criteria for identifying vital signs of potential clinical relevance are provided in Appendix 1.

In addition, the change from baseline in weight, BMI, and waist circumference, and potentially clinically relevant abnormalities in weight, will also be summarized.

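### The SAP does not separate home from clinic vital signs and weight, as it does for AISRS, and its Appendix 1 omits the supine restriction in protocol Appendix 3

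*Protocol*

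**What the plan says.** **Clinic method.** Protocol 3.7.4.4: "Blood pressure and heart rate measurements will be made in the supine and standing positions", after at least 3 minutes in each position, supine first.

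**Home readings.** COVID-19 addendum 4.1.1: "Blood pressure, heart rate, weight, and temperature may be measured as described in the protocol", with listed changes to device, time of day, and how results are reported and recorded. On the device: "Subjects will be asked to use their own collection device, if available". A device may also be supplied. The footnotes to addendum Tables 1.2-1 and 1.2-2 allow home collection at post-baseline and follow-up visits and ask for an appropriate device.

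**Baseline.** Addendum section 4: "If an in-person screening and baseline visit cannot be performed, then the subject cannot continue or be enrolled in the trial".

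**Analysis.** Addendum 2.5 leaves the effect of COVID-19 on the analyses to the final SAP. SAP 8.1 responds for one outcome, AISRS Total Score, summarised "by visit type (face-to-face vs. virtual) based on the Efficacy Sample". SAP 9.3 says: "Summary statistics for changes from baseline in vital signs will be provided for the Safety Sample". It also says: "Potentially clinically relevant vital signs measurements identified in the open-label treatment phase for the Safety Sample will be listed and summarized". Neither sentence mentions visit type or device. Table CT-1.5 counts face-to-face and virtual visits by week.

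**Flag criteria.** Protocol Appendix 3 marks the high limits of 140 mmHg systolic and 90 mmHg diastolic as Supine. SAP Appendix 1 gives the same limits without that word, in a section headed as criteria taken from the protocol.

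**The concern.** Protocol 1.3 names increases in blood pressure and heart rate, and orthostatic change, as possible effects of centanafadine. The vital-sign tables are where such effects would appear. A home value on a different device is compared with an in-person baseline, so the change includes any difference between devices. With no control arm, nothing in the trial shows how much of a shift in means or flags is device and how much is drug. SAP section 9 analyses safety data as observed cases and at the last visit, so one home reading can supply a subject's last-visit value. Weight is the most exposed, because its flag is a 7% change with no criterion value to meet as well.

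The missing word in SAP Appendix 1 is a separate problem. It applies at clinic visits too and does not depend on how many home readings there are.

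**Working it through.** The plan states no figure on this point, so there is none to reproduce.

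**1. Is there a rule for home readings?** SAP 9.3 covers the Safety Sample without exclusion. The proposed tables CT-11.2.1 to CT-11.5 carry no visit-type split, while CT-5.1.2 does so for AISRS. The documents therefore do not separate the readings. They do not say in words that the readings are pooled; that is the default reading of SAP 9.3.

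**2. What does omitting Supine do?** Under protocol Appendix 3, the two high limits apply to supine readings. Under SAP Appendix 1, they apply to a reading in any position. Every reading flagged under the protocol rule is also flagged under the SAP rule, and standing readings can be added. The omission can raise the incidence of these two flags but cannot lower it.

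**3. Which way could device error act?** This is an illustration only; every input is assumed and none comes from the documents. There is no drug effect. Each subject has a true level T ~ N(mean, between-subject SD). Baseline = T + e1. Post-baseline = T + e2 + bias + d. Here e1 and e2 have the visit SD and d has the device SD; bias and d are zero in clinic. A flag needs both the criterion value and the change from baseline. There were 2,000,000 draws per scenario, and the device SD ran from 3 to 8.

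| Flag | Assumed mean / between-subject SD / visit SD | Clinic | Home, bias −5 | Home, bias 0 | Home, bias +5 |
|---|---|---|---|---|---|
| Systolic ≥140 and rise ≥20 | 120 / 10 / 7 | 0.5% | 0.2–0.9% | 0.7–2.5% | 2.6–5.9% |
| Diastolic ≥90 and rise ≥10 | 76 / 7 / 5 | 1.4% | 0.4–2.7% | 2.2–7.4% | 8.7–16.2% |
| Heart rate >100 and rise ≥10 | 72 / 8 / 7 | 0.3% | 0.1–0.5% | 0.4–1.5% | 1.5–3.8% |

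With a bias of −5 and a small device SD, the home rate falls below the clinic rate. A real signal could be hidden as well as a false one created.

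**4. Weight.** Assume 80 kg, visit SD 1 kg and no scale bias. The flag needs a change of 0.07 × 80 = 5.6 kg. The SD of change is √(2 × 1² + s²), where s is the SD of the difference between scales. The rate is 2 × [1 − Φ(5.6/SD)]:

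- s = 0: SD 1.41, rate 0.01%
- s = 1: SD 1.73, rate 0.1%
- s = 2: SD 2.45, rate 2.2%
- s = 3: SD 3.32, rate 9.1%

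**5. Where is weight measured?** Addendum 4.1.1 lists weight among the measurements that may be taken at home. Protocol 3.7.4.3.1 places weight in the physical examination, and the footnotes to addendum Table 1.2-1 restrict post-baseline physical examinations to in-person visits. These passages do not agree.

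**The case against.** The addendum has safeguards. It keeps the protocol method apart from the listed changes, asks for an appropriate device, allows one to be supplied, and sends suspected errors to the medical monitor. Addendum 2.3 gives remotely performed assessments as an example of deviations recorded separately in eSource. Vital signs are additional safety variables in a descriptive trial whose primary endpoint is TEAEs. All of this stands and limits the weight of the point, but none of it is an analysis rule.

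Four stronger readings are tempting, and the documents do not support them.

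- **Home readings are in an unknown or single position.** No listed change waives supine and standing measurement. The fair statement is that no home position instruction or check is given.
- **Home devices are uncalibrated.** No calibration rule is stated either way.
- **Orthostatic flags are corrupted.** Those criteria compare a standing with a supine value, so an unpaired reading cannot meet them.
- **Home readings triple the flags.** With baseline fixed at 120 mmHg, 1 − Φ(20/SD) gives 2.3% at SD 10 and 7.7% at SD 14. The arithmetic is right, but the inputs are one chosen case. At a baseline of 110 the required rise is 30, and the rates are 0.1% and 1.6%. Moving from SD 10 to 14 implies added error of √(196 − 100) = 9.8 mmHg, about as large as the starting SD. Bias is left out, and downward bias can reduce flags.

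**Conclusion.** The point holds in two parts. First, the SAP gives no way to see whether vital-sign and weight results depend on where they were measured, although it does this for an exploratory efficacy score and the addendum had deferred such matters to it. Device error could move flags in either direction, and a single-arm trial cannot separate it from drug effect. The effect on trial totals cannot be computed: the share of home readings and the error SDs are not given, and the rates above rest on assumed inputs. A reader might infer that the safety tables are biased upward; the documents do not show that.

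Second, and more firmly, SAP Appendix 1 departs from protocol Appendix 3 on the two high blood-pressure limits. This needs no assumption about home readings. The weight passages are also inconsistent. All of this should be corrected, but none of it touches the primary TEAE analysis.

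**What to change.** 1. In SAP Appendix 1, restore Supine to the ≥140 mmHg systolic and ≥90 mmHg diastolic limits, so that they match protocol Appendix 3.
2. In SAP 9.3, keep all readings in the main vital-sign tables and listings. Add to CT-11.2.2, CT-11.2.3, CT-11.3 and CT-11.5 a split by visit type (face-to-face versus virtual) and a clinic-only sensitivity summary. Mark home readings in CT-11.2.1. Removing home readings from the main tables is not advised, because it could hide real abnormalities.
3. Reconcile addendum 4.1.1, protocol 3.7.4.3.1 and the in-person footnote of addendum Table 1.2-1 on where weight is measured.

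The cost is SAP wording and a few extra table columns. CT-1.5 already requires visit type, so the split should be feasible.

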4.1.2 Pregnancy

Pregnancy tests will be performed as described in the protocol at the time points defined in this COVID-19 Addendum Schedule of Assessments (Table 1.2-1) with the following changes:

- For planned visits that require a pregnancy test for females of childbearing potential (FOCBP), the site will provide the necessary tests and instructions so the test may be performed at home.
- Applicable subjects will perform a pregnancy test prior to dosing with IMP, ensuring a date and time-stamped picture or video of the result is taken. The subject will notify the site staff of the test results by telephone and send the time-stamped picture or video to the site staff by email.
 - If negative, site to inform the subject to proceed with dosing.
 - If positive, the site must instruct the subject to immediately stop taking IMP, and the site will refer to the Pregnancy section of the protocol for appropriate immediately reportable event reporting.
 - Further instruction must be agreed upon in consultation with the sponsor.

4.2 Clinical Outcomes

4.2.1 General Considerations

Attempt to standardize the method of administration for a scale across subjects (eg, video chat or telephone) to decrease variability, and consult trial-specific guidance for recommendations on preferred methods for a given outcome. Prior to starting the remote visit, the subject should be informed of the estimated amount of time the visit is expected to take, and confirm subject access to a sufficient mobile or Wi-Fi signal and that the subject's device has an adequate charge. Any potential distractions should be addressed proactively to ensure the subject is not distracted during the remote visit. Assessments should be administered by the same qualified/trained rater who rated the subject previously; if this is not possible due to staff availability and/or technological limitations, discuss relevant information with previous raters to obtain clinical context (note that per protocol, raters must be trained/qualified to conduct assessments in all cases). Do your best to conduct all assessments during the same call/video chat, on the same day. Video chat is the preferred method for the Adult ADHD Investigator Symptom Rating Scale (AISRS), while other assessments can be completed by telephone or video chat.

All site staff will adhere to all Good Clinical Practice Guidelines, including Good Documenting Practices. Any factors that may potentially affect the subject's report (eg, unavoidable distractions, rater assessment of subject's level of engagement, any unexpected modifications to procedures) should be documented in eSource, along with how an assessment was completed (eg, via video, telephone, etc) and any modifications or accommodations performed. All assessment start times should be documented (including those that are interview based). If any AE-related information is reported, standard procedures for remote AE assessments with evaluation and follow-up with the medical monitor, as necessary, should be followed and documented accordingly.

4.2.2 Semi-Structured Interviews

Those administering scales must follow scale administration, training guidelines, and rating conventions as much as possible as provided by the sponsor, and ensure they maintain neutrality/research rapport as usual. Careful attention must be provided to subject engagement to try to ascertain whether the subject is distracted or minimizing, and efforts must be made to redirect the subject and ask additional questioning, if needed. Things to pay attention to are, but not limited to, the following: tone of voice, cadence, volume, and rate of speech if visual cues are not available (ie, if administered by telephone). Assessment start-stop times will be documented in eSource. The interviewer will be asked to "Rate what you see" and "Rate what you hear", and should not discount

Confidential - Proprietary Information

17

symptoms on the assumption that they are caused or exacerbated by COVID-19 or changes in life circumstances.

4.2.3 Subject or Caregiver Reported Outcomes

Patient-reported outcomes (PROs) are to be completed by subjects on paper rather than be administered by raters over the telephone or teleconference platform. The subject should complete the paper scale during the telephonic/video conference assessment visit to ensure the correct date and time for PRO completion. It is recommended to use the video conference platform to observe the subject completing the paper PROs in a manner that does not allow the site staff to see the subject's responses but rather to ensure that the ratings are completed by the subject themselves. If this is not feasible, before ending the assessment visit, ask the subject to check if they have completed the PRO forms and to check again for completeness. Documentation must clearly detail the mode of administration and data entry. All assessments, including paper reports, should be completed during the telephonic/video conference visit.

4.2.4 Global Assessments of Severity and Subject Status

Sites will use all available sources of information to complete global assessments of severity, change/improvement, or subject status (eg, subject report, informant report, medical records if available, other assessment data if allowed per protocol). Site staff will be asked to conduct a general relatively unstructured evaluation and utilize informants as needed, ensuring that informants are also in a quiet and private place during evaluation. Attempt to complete global assessments after other assessments have been completed so all information from the visit is available, if allowed per protocol and per sponsor team instruction. The raters will be asked to "Rate what you see" and "Rate what you hear", and not rate according to what might be reasonable/expected due to COVID-19 as the rater must make a clinical assessment of subject status regardless of cause.

